We propose a pre/posttest, RCT with a 4-step (12 months per step), stepped-wedge design³ to compare effects of usual outpatient palliative care (usual care) and usual care along with either nurse-led or chaplain-led DT on patient outcomes (dignity impact, existential tasks [preparation for death, life completion], cancer prognosis awareness [peaceful awareness, treatment preferences]). We will assign 6 outpatient palliative care sites to usual care during the first-step, and randomly assign two sites per step to begin and continue DT led by either a nurse or a chaplain during each of the next 3 steps. During the usual care steps, 280 patients will complete pretest measures (patient outcomes, covariates [physical symptoms, spiritual distress], and satisfaction with palliative spiritual care services), receive usual palliative care, and complete posttest measures (patient outcomes, covariates, satisfaction). During the experimental steps as part of routine palliative care service delivery, 280 patients will complete pretest measures, receive nurse-led or chaplain-led DT, and complete posttest measures. Using mixed level analysis with site, provider (nurse, chaplain) and time (step) included in the model, we will compare the usual care and each of the DT groups for effects on dignity impact, existential tasks, and cancer prognosis awareness and explore the moderating effects of physical symptoms and spiritual distress. We will also determine the effect of usual care and DT on the patient's satisfaction with palliative spiritual care services and the report of the patient's unmet spiritual needs.

Specific Aims:

In a diverse sample of 560 elderly cancer patients, the specific aims are to:

Aim 1. Compare usual care and usual care with nurse-led or chaplain-led DT groups for effects on:

a) patient outcomes (dignity impact, existential tasks [preparation for death, life completion], cancer prognosis [peaceful awareness, treatment preferences]). We hypothesize that, controlling for pretest scores, each of the DT groups will have higher scores on the dignity impact (1° outcome) and existential tasks (2° outcome) measures than the usual care group. Also patients in each of the DT groups will report better peaceful awareness and treatment preferences more consistent with their cancer prognosis (2° outcomes) than the usual care group; and

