b) processes of delivering palliative spiritual care services (satisfaction and unmet spiritual needs; 2° outcomes). We hypothesize that each of the DT groups will show increased patient satisfaction with spiritual care services and fewer unmet spiritual needs compared to the usual care group.

Aim 2. Explore the influence of physical symptoms and spiritual distress on the dignity impact and existential tasks effects of usual palliative care and nurse-led or chaplain-led DT. We hypothesize that physical symptoms and spiritual distress will significantly affect intervention effects. This rigorous trial of DT will constitute a landmark step in gero-oncology palliative care and spiritual health services research.

Study design:

We propose a 6-site, pre/posttest, randomized, controlled 4-step, stepped-wedge design to compare the effects of usual outpatient palliative care and usual outpatient

palliative care along with nurse-led or chaplain-led DT on patient outcomes and palliative care processes. We will assign the 6 sites to usual care during the first-step period (10 months), and randomly assign 2 sites per step to begin and continue DT during each of the next 3 steps (10 months each).

Figure 1 shows the stepped-wedge study design with projected numbers of

completed patients needed per site, step period, and group (usual care, DT led by either a nurse or a chaplain). [name], a highly qualified statistician will conduct the randomization of site to steps 2-4. Each step will be 10 months long, with DT training during a 1-week period between steps. For each site/step, a quota of 50% of the participants will report low or high distress on the Personal Dignity Inventory to assure we recruit a sample with a range of problems threatening their dignity. Each patient will participate for 4-6 weeks. Over the 10 months at each step, we expect 23-24 patients to participate at each site (93-94 total patients per site).

Figure 1. Stepped-wedge design	N per step per site			Total N
Site 6	23	23	23	24 93
Site 5	23	23	23	24 93
Site 4	24	23	23	24 94
Site 3	24	23	23	24 94
Site 2	24	23	23	23 93
Site 1	24	23	23	23 93
Step	1	2	3	4
Patients/				
Step Period	142	138	138	142 560
Usual Care				280
Nurse-Led DT				140
Chaplain-Led DT				140
Step Period Duration (mo)	10	10	10	10 40

Subject identification, recruitment and consent:

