We will recruit the study sample from the population served by the six hospitals participating in this application. The sites represent the South Eastern (Emory University, UF Health Gainesville), North Midwest (Northwestern University, Rush University), South Midwest (MD. Anderson), and Western (University of California at San Francisco) areas of the U.S. The participants will be elders who are diagnosed with cancer and are receiving outpatient palliative care services at the participating sites. At UF Health, we will recruit the sample from the existing outpatient oncology palliative care services and those under development within the UF Cancer Center.

The consent process will be completed in person and in a private area at the outpatient palliative care services of the 6 sites, or at another outpatient palliative care site or other private location chosen by the potential subject to go over the details of the study and informed consent. The consent process may also be conducted by phone with the signed consent form returned by mail in a preaddressed, stamped envelope.

Procedures:

The study will be conducted in the outpatient clinic in spaces available for research or virtually via a HIPAA-compliant video-conferencing platform. The investigators will attend patient care planning meetings and introduce the study to the palliative care team members. Any member of the palliative care team will refer patients to the RA on the day the patient is seen in the palliative care clinic or via a HIPAA-compliant video-conferencing platform.

Figure 2 shows the general flow of patients through the outpatient palliative care clinics and study procedures for this study of nurse-led or chaplain-led DT over 4-6 weeks. Prior to participant recruitment, the research assistants (RA) will be trained in all study procedures. Prior to stepping up to the DT steps of the study, the nurse and chaplains at the sites scheduled to begin the DT will be trained in the DT.

Study Procedures:

- I. The RA will recruit the referred and potentially eligible patients for this study, provide and obtain informed consent, determine final eligibility, and schedule time before the next clinic visit or at a time convenient to the patient for the patient to complete the pretest tools via an audio-recorded interview documented on REDCap forms and stored on REDCap for quality control purposes.

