- II. Then the RA will inform the nurse/chaplain that the patient is available for care (usual care or DT, depending on the study step and site). The nurse/chaplain will provide the designated care on the same day as the pretest data collection, as specified in the following section:
 - a. Usual care. Palliative care nurses usually see patients each clinic visit to assess vital signs, function, symptoms, and to provide patient and family education. They document findings and interventions in the electronic health record (EHR). Whereas usual care for palliative care chaplaincy in the outpatient setting varies by site, chaplaincy care for usual care patients in this study will follow the usual practice for inpatient palliative care chaplaincy, which is to visit all new referrals to the clinic and assess their spiritual and religious needs. This assessment is then memorialized in a spiritual treatment plan documented in the EHR.
 - b. Dignity Therapy. The DT intervention is detailed in [name]'s manualized guide; he serves as our co-investigator and will conduct trainings for the team. The basic questions of the DT interview appear in Table 2. The nurse-led or chaplain-led DT intervention involves three sessions, each of which follows a set process (Fig 2). The standardize approach to the delivery of the intervention facilitates a personal process of reflection and recognition that allows the patient to make meaning of their experience.

[figure not shown]

Table 1. Examples of the Dignity Therapy Question Protocol

1. Tell me about your life history; particularly the parts that you either remember most or think are the most important? When did you feel most alive?
2. Are there specific things that you would want your family to know about you, and are there particular things you would want them to remember?
3. What are the most important roles you have played in life (family roles, vocational roles, community service roles, etc.)? Why were they so important to you, and what do you think you accomplished in those roles?
4. What are your most important accomplishments, and what do you feel most proud of?
5. What are your hopes and dreams for your loved ones?
6. What have you learned about life that you would want to pass along to others?
7. What advice or words of guidance would you wish to pass along to your [son, daughter, husband, wife, parents, other(s)]?

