8. Are there particular things that you feel still need to be said to your loved ones, or things that you would want to take the time to say once again?
9. Are there words or perhaps even instructions you would like to offer your family, in order to provide help to prepare them for the future?
10. In creating this permanent record, are there other things that you would like included?

When the nurse/chaplain session(s) are completed, the nurse/chaplain will inform the RA that he/she has completed all nurse/chaplain session(s). The interview will be conducted either in person in the clinic or at a time and place convenient to the patient (e.g., home, community setting), or via a HIPAA-compliant video-conferencing platform.

III. Either in-person if the patient has a clinic visit, by telephone contact or via a HIPAA-compliant video-conferencing platform, the RA will schedule the follow-up appointment at a time and place convenient to the patient (e.g., clinic, home, community setting), and complete the audio-recorded posttest measures within 5-10 days. Upon completion of posttest measures, the RA will provide \$50 (cash or card) to the patient for time and travel expenses to complete study measures.

Sample size:

We will recruit 1500 adults with cancer diagnoses who are receiving care from the outpatient palliative care services of the six hospitals. From this sample, 560 patients will complete the study and provide data for analysis, 280 for the DT groups (140 per each of the two DT groups) and the 280 for the control groups. From UF Health, we expect to recruit 94 total patients, 23-24 per year with complete data. We will consent approximately 1,500 (250 total patients per site) for screening over the 4.5 years devoted to data collection and 120 to participate to achieve a completed sample of 94 patients per site.

Anticipated risks:

The risks of this study are primarily those regarding potential for fatigue from completing the questionnaires and the intervention, the emotionally evocative nature of the material shared during the course of the intervention, and loss of privacy. The likelihood of these risks is low, as has been observed and documented in the many previous studies of DT cited in the Background section.

Anticipated benefits:

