To ensure confidentiality, each subject and provider (nurse or chaplain interventionist) will be assigned a code number. All data are coded with the code numbers and linked to the patient's name. The patient's name is removed from the database when statistical analyses are conducted. Demographic information, chart review information, and other self-report outcomes are entered into data forms in REDCap, an Internet-based data management system. The REDCap system has strong password protection and is located on a reliable and secure research server at UF. Access to the server is password restricted and only the pertinent research staff can access the data via an application designed for data download. Only the data manager and statistician will have authority for direct access to the database server files. Participants or study staff will enter data through the REDCap system designed specifically for this study on a tablet computer with strong password protection. The team members in the Center for Palliative Care Research and Education at the UF are skilled in developing and deploying user-friendly, secure, and reliable programs for data collection and tracking. The staff members in the nursing information systems office are well-trained and responsible for maintaining the network security and adhering to UF policy regarding security for research data and protected health information. The UF Health Sciences research servers have firewall protection and access through the firewall is restricted and closely monitored. Data on the server will be backed up each night; backups are stored nightly in water- and fireproof cabinets. The tablets used for data collection will be locked in a secure cabinet when not in use. The project statistician will monitor the safety of the data continuously.

Completing the self-report measures and the DT intervention are low risk. Continuous, close monitoring by the Multiple Principal Investigators (MPIs) will be an adequate and appropriate format for monitoring, with prompt reporting of adverse effects to the IRB and NIH Program Officer. As a low-risk study, data monitoring by the MPIs would meet the NIH requirements for

data safety and monitoring for a clinical trial. The co-investigators, site directors, and other team members are well positioned clinically to identify any adverse event and report it to the MPI [name], who will report it to other MPIs, the IRBs and NIH program officer.

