Aim 1. Linear mixed effects models will be used to compare the effects of usual palliative care with usual palliative care with nurse-led and chaplain-led DT groups on (a) patient outcomes and (b) processes of delivering palliative spiritual care services. Random effects terms will be used to model the variations between sites. A main challenge of data analysis of a stepped-wedge design is the modeling of potential time trends. We plan to treat time as a continuous variable and utilize smoothing splines to model potential time trends. Smoothing splines is a nonparametric method that allows flexibility to model different time trends without overfitting by enforcing a smoothness constraint. Likelihood ratio tests will be used to determine the statistical significance of the intervention effect on various outcome measures. We hypothesize that, controlling for pretest scores, patients in both nurse-led and chaplain-led DT groups will have higher dignity impact scores, higher preparation for death and life completion scores, better peaceful awareness, and treatment preferences more consistent with their cancer prognosis than the usual care groups. We also expect the patients in the DT groups to be more satisfied with the palliative care and have fewer unmet spiritual needs than the usual care groups. We do not expect significant difference between nurse-led and chaplain-led DT interventions. Note that, this does not necessarily mean that the two interventions are equally effective. We do not seek to test the equivalence of the two intervention arms. At this point, it is premature to speculate on their relative efficacy. We expect most patients in this study to have metastatic cancer. If a sizable portion of our sample has non-metastatic cancer, we will explore if they respond to DT differently than those with metastatic disease.

Aim 2. The effect of physical symptoms and spiritual distress on the dignity impact and existential tasks will be modeled nonparametrically using smoothing splines. Our models will include both main effect for physical symptoms and spiritual distress and their interactions with the intervention. This analysis will provide insight on the type of patients most in need of and most likely to benefit from the DT intervention. Likelihood ratio tests will be used to determine the significance of the interaction. We hypothesize that patients' levels of spiritual distress and physical symptom scores will moderate the intervention effect.

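### The stated models have random effects for sites only and leave "provider" undefined, so differences between individual DT interventionists may be missing from the standard errors of the DT effects

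*Combined protocol and SAP*

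**What the plan says.** Three places in the protocol bear on this.

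- **Data analysis, Aim 1** specifies linear mixed models with likelihood ratio tests: "Random effects terms will be used to model the variations between sites". It names no other random effect and does not mention provider.
- **Background and Purpose**, design paragraph, lists more terms: "Using mixed level analysis with site, provider (nurse, chaplain) and time (step) included in the model". It does not say whether provider is fixed or random.
- **Data collection and management** uses the same word for the person: "each subject and provider (nurse or chaplain interventionist) will be assigned a code number". The identifier is therefore recorded, but no stated analysis clearly uses it.

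On delivery, Study Procedures says "The nurse-led or chaplain-led DT intervention involves three sessions". Before a site crosses over, "the nurse and chaplains at the sites scheduled to begin the DT will be trained in the DT". The number trained per site is not given.

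**The concern.** DT is an interview-based intervention given over several sessions by a limited number of trained people. Patients of the same interventionist share that person's skill, so their outcomes may be correlated. A site intercept is common to a site's usual-care and DT periods. It removes whatever is stable at the site, but not a component that appears only after crossover. That component shifts the within-site contrast from which the DT effect is estimated.

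If it is left out of the model, variation between interventionists is not counted as uncertainty about DT. One or two unusually good or poor nurses could then carry the nurse-led result, and the test would treat their influence as a replicated effect of DT. The primary outcome is exposed because each DT arm is compared with usual care separately.

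**Working it through.** **Plan's own figures.** The protocol gives no power, SD or ICC to reproduce, but the arm totals can be checked. Cell sizes come from Figure 1 ("we expect 23-24 patients to participate at each site" in each step) and the allocation rule is "randomly assign 2 sites per step to begin and continue DT during each of the next 3 steps".

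- Usual care: 142 + 92 + 46 = 280.
- DT: 46 + 92 + 142 = 280.
- With one nurse-led and one chaplain-led site in each crossover pair (an assumption), each discipline gets 140.

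This agrees with "280 for the DT groups (140 per each of the two DT groups) and the 280 for the control groups".

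**Model.** Total variance is set to 1, so standard errors are in outcome SDs. Let X hold the step effects and one DT indicator per discipline. The true covariance is

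V = σe²I + σs²·ZsZs′ + σp²·ZpZp′,

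where Zp is zero outside DT periods. The site-only analysis uses W = σe²I + σs²·ZsZs′. With A = (X′W⁻¹X)⁻¹, the reported SE is √Ajj and the true SE is √(A X′W⁻¹VW⁻¹X A)jj.

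**Assumed inputs.** Site ICC 0.02 or 0.05; interventionist ICC (σp²) 0.02, 0.05 or 0.10; one, two or three interventionists per site.

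**Result: true SE divided by site-only SE, for one discipline's DT effect**

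| Interventionists per site | Site ICC | ICC 0.02 | ICC 0.05 | ICC 0.10 |
|---|---|---|---|---|
| One | 0.02 | 1.13 | 1.31 | 1.58 |
| One | 0.05 | 1.11 | 1.28 | 1.52 |
| Two | 0.02 | 1.07 | 1.17 | 1.32 |
| Two | 0.05 | 1.06 | 1.15 | 1.29 |
| Three | 0.02 | 1.05 | 1.11 | 1.23 |
| Three | 0.05 | 1.04 | 1.10 | 1.20 |

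**Hand check (site ICC 0.02, interventionist ICC 0.05).** The site-only SE is 0.160. With one interventionist per site, a discipline's effect rests on three people, so the added variance is at least σp²/3 = 0.05/3 = 0.0167. Then √(0.160² + 0.0167) = √0.0423 = 0.206, a ratio of 1.29. Unequal weights raise the SE to 0.210 and the ratio to 1.31. With two per site, √(0.0256 + 0.05/6) = 0.184, a ratio of 1.15, against 1.17 in full.

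**Sensitivity to the reported SE.** The table gives the site-only model none of the interventionist variance. If its residual takes up all of that variance, the reported SE is 0.164. At site ICC 0.02 the ratios become 1.12, 1.28 and 1.52 (one per site) and 1.06, 1.14 and 1.27 (two).

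**False rejection.** Likelihood ratio test of nurse-led DT at nominal 5%, no true DT effect, site-only model, interventionist ICC 0.02, 0.05 and 0.10:

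- One per site: 9.5%, 12.8%, 19.6% with site variance 0.05 (8,000 trials); about 9%, 14%, 22% with 0.02 (3,000 trials).
- Two per site: 8.1%, 10.0%, 13.4%; about 8%, 10%, 14%.
- Three per site: 7.5%, 8.6%, 11.0% (site variance 0.05 only).
- No interventionist effect: 6-7%. Only the excess over this belongs to the present point; the 6-7% itself reflects having six sites.

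**The case against.** A reader might infer that the plan ignores interventionists altogether and that its intervals are certain to be too narrow. The documents do not support that, for four reasons.

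1. **Provider is in the design summary's model.** The data-collection section uses the word for the coded individual. If that is the meaning and the term is random, the point is largely met. The two-level parenthesis, and the comparison of usual care with each DT group that follows it, make discipline the more natural reading, but nothing settles it. A discipline term only separates the two DT arms and does not model correlation among one nurse's patients.
2. **The clustering need not be confined to DT.** Study Procedures has nurses and chaplains delivering usual care too, possibly the same people. With one provider per site and the same effect in both periods, the site intercept absorbs it and the ratio is 1.00. With half the provider variance shared, the ratios fall to about 1.04-1.24 (two per site) and 1.07-1.44 (one). This stands as a real reduction. However, the tasks differ: routine assessment and education against a manualized life-review interview. A DT-specific part is therefore plausible.
3. **The plan's wording on random effects is plural.** It does not exclude a random site-by-DT term, which would do the same job with one interventionist per site. It does not state one either.
4. **The size rests on undocumented inputs.** If both disciplines work at every site, one person each, the ratios at site variance 0.05 are 1.06, 1.15 and 1.28. Manualized delivery and common training argue against treating ICC 0.10 as typical.

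**Conclusion.** The point holds conditionally. No passage commits to a random effect for the individual interventionist, and the two descriptions of the model do not agree on provider. If interventionists differ in a way specific to DT periods, the site-only standard errors are too small. The true SE is then about 1.04-1.32 times the reported one with two or three interventionists per site, and 1.11-1.58 times with one, at interventionist ICC 0.02-0.10 and site ICC 0.02-0.05. It ranges down to no inflation if provider effects are fully shared with usual care.

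False-positive rates near 20% should not be read as the expected figure: they need one interventionist per site and an ICC of 0.10. With two or three per site and an ICC of 0.02-0.05 the rate is 7.5-10.0%, an excess of 1.0-3.5 points over the 6.5% found with no interventionist effect at site variance 0.05. The change is still worth making: it is cheap, it bears on the primary comparison, and it improves on the site-only model.

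**What to change.** Reconcile Background and Purpose with Data analysis. State whether provider means discipline or the coded individual, and how it enters the model. Then add to the Aim 1 and Aim 2 models a random effect for the coded DT interventionist, nested in site and acting in DT periods (zero for usual-care patients). Where a site has only one interventionist, this is the same as a random site-by-DT effect, and the plan should say so. Keep the site effect, and report the interventionist variance with each DT effect.

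The cost is one model term using codes already collected, and somewhat wider intervals for each DT arm. In the simulations with site variance 0.05, the added term brings false rejection to 6.4-6.9% with two or three interventionists per site, essentially the six-site baseline. With one per site it remains at 7.6-10.4%, because the variance is imprecisely estimated. The correction there is only partial.

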There may be no benefit to individual participants in any arm since this study is needed to understand how DT can be implemented in a real-world setting and still retain its beneficial impacts. A common perception regarding DT is that it has been sufficiently studied that it should simply be accepted. However, there is minimal knowledge on how DT fares in the real world setting. As our recent systematic review has revealed, results of many feasibility studies are very promising, but only one small efficacy study showed significant effects on study outcomes whereas the other three completed efficacy studies, one with more than 400 patients, did not show significant effects on study outcomes. Our study will fill the gap of inconsistent and inconclusive effects, in turn then allowing for the next step of up-scaling implementation.

The multiple feasibility or efficacy studies have shown that DT is greatly appreciated by participants, families and healthcare providers. So there seems reason to believe that DT's impact on promoting healthy life transitions will result in a patient benefit for those from either of the nurse- or the chaplain-led DT arms.

The study has tremendous potential to inform future studies on DT and advancing DT to clinical palliative care practice involving elderly patients with cancer. There tends to be a bias regarding psychosocial interventions, which includes the idea that these interventions ought to be resource neutral i.e., without any cost whatsoever. However, the availability of resources should be driven by efficacy and the evidence to support the application of DT in a given setting. This study will provide needed data on how to apply DT in specific services – by the nurse or chaplain.

The study also has tremendous potential to help the scientific community understand ways for spiritual palliative care services to be implemented systematically to affect patient outcomes and care processes. Very few spiritual care interventions have been systematically developed, protocolized, and studied. DT is one of them. Until we understand how much of DT's impact is spiritual, we do not know how to use DT as a tool to study spiritual care needs.

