The MPIs ([name], [name], [name]) will evaluate the progress of the study, including periodic assessments of data quality and timeliness, participant recruitment, accrual and retention, participant risk versus benefit, and other factors that could affect study outcomes. The MPIs also monitor for scientific or therapeutic developments that may have an impact on the safety of the participants or the ethics of the study. The MPIs make recommendations to the IRB and the site directors concerning continuation or conclusion of the trial.

Data analysis:

Data management and preliminary data analysis procedures will be supervised by MPI [name] and conducted by [name], the Co-I and statistician, using statistical software R. Data will be stored in a REDCap database and will be exported to R. In the case of missing data, multiple imputations will be used to generate multiple complete datasets on which statistical inference will be performed. Missing at random assumption will be assessed and if necessary sensitivity analysis will be performed using pattern mixture methods. We will consider a p value less than .05 as statistically significant.

Descriptive statistics (ranges, frequencies, means, and standard deviations) and graphic summary (box plots, histograms, bivariate scatter plots, etc.) will be first generated for both patient covariates and outcome measures. We will check patient characteristics to see if there is notable imbalance between the three arms, as well as whether there is significant variations between sites or over time. Descriptive statistics of patient outcomes and process data will reveal patients' spiritual state, identify potential areas for improvement in nurse and chaplain service, and provide information on nurses' and chaplains' workload both in usual care and when dignity therapy is added and on family-related variables (e.g., legacy document disposition, etc.).

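### Aim 1 tests DT effects across six randomised sites by a likelihood-ratio test with no small-sample reference and no stated site-by-step term; its error is about 5-7% per DT group, or 7-10% if site levels drift between steps

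*Combined protocol and SAP*

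**What the plan says.** Study design: the randomised units are six sites, and the plan is to "randomly assign 2 sites per step to begin and continue DT during each of the next 3 steps".

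Data analysis, Aim 1: linear mixed models compare usual care with nurse-led and chaplain-led DT. On random effects the section says only "Random effects terms will be used to model the variations between sites". Time is to be continuous, with a smoothing spline. The hypothesis adjusts for baseline: "We hypothesize that, controlling for pretest scores, patients in both nurse-led and chaplain-led DT groups will have higher dignity impact scores". The test is given as "Likelihood ratio tests will be used to determine the statistical significance of the intervention effect on various outcome measures". The opening of Data analysis sets significance at p < .05 and, for missing data, says "multiple imputations will be used to generate multiple complete datasets on which statistical inference will be performed".

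Two other places bear on the model. Background and Purpose has "Using mixed level analysis with site, provider (nurse, chaplain) and time (step) included in the model". Data collection and management uses the same word for the individual: "each subject and provider (nurse or chaplain interventionist) will be assigned a code number".

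The documents do not state the reference distribution of the likelihood-ratio test, whether site-by-step or site-by-DT random terms are included, how tests are pooled over imputations, or whether conclusions are meant for these six sites or for others.

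**The concern.** A chi-square reference for a likelihood-ratio test is a large-sample result, and here the number that has to be large is the number of sites. With six, the variance components are poorly estimated and the test treats them as known. If the model also omits variation that is present, such as a site's level moving between steps, patients in the same site and step count as more independent than they are. The standard error is then too small.

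This is the only test stated for dignity impact, the primary outcome. An error rate above the nominal 5% would make a positive result for either DT group less secure than its p value suggests. Because the model cannot be programmed uniquely from the text, the choice of random terms could also be made after the data are seen.

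**Working it through.** **1. Layout (Figure 1).** Take sites 1-2, 3-4 and 5-6 as crossing over at steps 2, 3 and 4.
- DT cells: 2×(23+23+23) + 2×(23+24) + 2×24 = 138 + 94 + 48 = 280.
- Usual care: 560 − 280 = 280.
- With one nurse-led and one chaplain-led site per crossover, each DT group has 69 + 47 + 24 = 140.

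This reproduces 280/140/140. An even split of leader types within every site gives 280/2 = 140 as well, so the figure does not settle the layout. The documents give no power, SD or ICC to reproduce.

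**2. Planned test as read here.** posttest = β₀ + β₁·pretest + f(step) + δ_N·nurse DT + δ_C·chaplain DT + u_site + e, fitted by ML. Each δ is tested by 2(ℓ₁ − ℓ₀) against chi-square with 1 df (critical value 1.96² = 3.84).

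**3. Assumed inputs.** Units are total posttest SD, with a pre-post correlation of .6. Site variance = ICC×CAC and site-by-step variance = ICC×(1 − CAC), where CAC is the between-step correlation. ICC .05 with CAC .8 gives .04 and .01; ICC .10 with CAC .5 gives .05 and .05. Drift is shared by pretest and posttest.

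**4. Null rejection per DT group, complete data, one leader type per site.**

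| Truth | Step indicators / spline |
|---|---|
| Only site levels vary, ICC .05 | 6.9 / 6.2% |
| Drift, ICC .05, CAC .8 | 7.3 / 7.1% |
| Drift, ICC .10, CAC .5 | 9.5 / 8.5% |
| DT effect varies by site, SD 0.1, averages zero over each group's three sites | 7.1 / 7.0% |
| Same, SD 0.2 | 6.4 / 6.7% |
| DT effect varies by site, SD 0.1, zero only in a wider population | 9.6 / 9.0% |
| Same, SD 0.2 | 16.1 / 16.9% |

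Monte Carlo SE is √(p(1−p)/R). For 6.9% on 4,000 replicates it is √(.069×.931/4000) = 0.4 points. For 16.1% on 1,500 it is √(.161×.839/1500) = 0.9 points.

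Separately coded runs agree:
- Site levels only: 6.5%; without the pretest covariate, 5.2-6.6% over ICC .01-.20.
- Drift: 7.0-7.2% (milder) and 8.0-10.0% (stronger).
- Wider target, SD 0.2: 15.9%.

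With both leader types in every site, the wider-target error is 7.8% at SD 0.1 and 11.5% at SD 0.2, against 9.3% and 15.3% with one type per site in the same run. If the between-site wording is read to include a random DT effect by site, the chi-square test still gives 7.0 / 6.6% at SD 0.1 and 11.1 / 10.5% at SD 0.2 (wider target).

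**5. After imputation.** Sample size gives 120 participants per site for 94 completers: 6×120 = 720 enrolled, with 26/120 = 22% of posttests missing (here dependent on pretest). Ten imputations were used.
- Likelihood-ratio tests pooled by D2: 4.2-5.2% with site levels only; 5.6-8.0% with drift; 13% with a wider target at SD 0.2.
- Wald tests pooled by Rubin's rules without small-sample df: 6.3-6.4%, 6.4-8.6% and 15.4-15.5% in the same order (ICC .05 for the first).

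**6. Alternative test.** With drift, the information lies in 24 site-by-step cells. After 6 site, 3 step and 2 DT parameters, 24 − 11 = 13 df remain. Complete-data null rejection for REML with a Satterthwaite t test:
- Site and site-by-step terms: 3.7-6.1% over six scenarios (model right, drift, six-site null).
- Site intercept alone: 5.5-9.2% in the same six, so the df correction by itself is not enough.
- Site-by-DT term added: 3.3-6.4% over six scenarios (model right, drift, wider null), but 0.9-1.6% at SD 0.2 when the target is the six sites.

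Pooled by Rubin's rules with Barnard-Rubin df over imputations drawn from site-by-step cells, these tests reject only 0.8-3.4%. A comparable cell-level t test on complete or observed cases gave 4.3-5.2%.

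**The case against.** The strongest case against is that the plan's inference runs on imputed data, and with D2 pooling the base-case excess is gone (about 5%). That stands: with no drift, whether the test is liberal depends on a pooling rule the plan does not name. It does not remove the drift result, which stays at about 6-8% under D2.

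The documents also do not name chi-square; it is the usual default for such a test, and the figures are conditional on it. *Provider*, set beside the three arms in Data analysis, most naturally means leader type. The plan should still say so.

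A reader might infer three stronger things.
- *That the error is really 9-17%.* This needs a target beyond the six sites. The only hint is "in turn then allowing for the next step of up-scaling implementation", which stands under Anticipated benefits and defines no inferential target. The recruitment section draws the sample from the population the six hospitals serve. The size also depends on a DT-effect SD that the documents do not give.
- *That each DT group rests on three sites.* The 140/140 split fits that layout, but it equally fits both leader types in every site.
- *That drift pushes the error to 18.8%.* Figures of that size come from a simulation without the pretest covariate. The plan adjusts for pretest, which absorbs much of any drift that pretest and posttest share.

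Finally, a small-sample t test pooled over imputations can miss 5% by more than the planned test does. That also stands, and it shapes the fix.

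**Conclusion.** The concern holds in a limited form. The stated test has no small-sample reference for six randomised sites, and the random-effects structure is not fully specified.

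- Only site levels vary: about 5-7% per DT group on complete data, and about 5% under D2 pooling.
- Site levels drift between steps: about 7-10% on complete data and about 6-8% under D2. This needs no wider target.
- DT effects differ by site and the target is wider: about 9-17% at SD 0.1-0.2 with one leader type per site, and about 8-12% with both types in every site. This is conditional, because the plan does not state its target.

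The absolute levels rest on the assumed ICC, between-step correlation, DT-effect SD, pre-post correlation and leader layout, and on drift being shared by pretest and posttest. The point is worth settling before analysis. It does not call the design or the patient numbers into question.

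**What to change.** In Data analysis, Aim 1, for outcomes modelled as continuous:

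1. State whether inference is to these six sites or beyond, and what *provider* means in the model.
2. Keep the pretest adjustment. Fit by REML with random site and site-by-step terms, in R `(1|site) + (1|site:step)`. Replace the likelihood-ratio test with a Satterthwaite (or similar small-sample) t test for each DT group. Name one form for time; step indicators and the spline both performed acceptably.
3. Add a random site-by-DT term, `(0+DT|site)`, only if the plan states a target beyond the six sites.
4. Apply the test to patients with an observed posttest. This is valid if missingness depends only on pretest and the other modelled terms. Keep multiple imputation as a sensitivity analysis, or choose an imputation and pooling rule that has been checked by simulation on this layout.

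**Cost.** Wording and a few lines of R, with no change to conduct or recruitment. Multiple imputation moves from the main analysis to a supporting one unless a checked rule is found. On complete data, the six-site version has intervals 1.12-1.25 times as wide as the planned model's. At the effect where the planned test has nominal 80% power, its power is 63-74%; part of that gap is the planned test's excess error and part is real loss. The wider version costs more: 1.17-1.31 times with no site-specific effect and 1.51-1.55 times at SD 0.2, with power of 63-67% and 51-53%. The documents state no power figure that this would contradict.
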